10.9 Patient Reported Outcomes

The SF-36v2 is a general Health Related Quality of Life (HRQoL) instrument with extensive use in a broad variety of health conditions and is the standard in literature for HCV. The SF-36v2 instrument comprises 36 total items (questions) targeting a subject's functional health and well-being in 8 domains (physical functioning, role physical, bodily pain, general health, vitality, social functioning, role emotional and mental health). Domain scores are also aggregated into a Physical Component Summary score and a Mental Component Summary score. Higher SF-36v2 scores indicate a better state of health.

The TSQM is a 14-item instrument and includes assessments of satisfaction with a medication's effectiveness (Effectiveness, three items), lack of side effects (Side Effects; five items), convenience (three items) and the subject's global satisfaction (Global Satisfaction; three items). TSQM scores range from 0 – 100 with higher scores indicating better satisfaction.

The EQ-5D-3L is a health state utility instrument that evaluates preference for health status (utility). The 5 items in the EQ-5D-3L comprise 5 dimensions (mobility, self-care, usual activities, pain/discomfort, and anxiety/depression) each of which are rated on 3 levels of severity. Responses to the 5 items encode a discrete health state which is mapped to a preference (utility) specific for different societies. Subjects also rate their perception of their overall health on a separate visual analogue scale (VAS).

The mean change from baseline to each applicable post-baseline timepoint in the SF-36v2 Mental Component Summary (SF-36-MCS) and Physical Component Summary (SF-36-PCS) scores; EQ5D-3L health state index and VAS score will be summarized descriptively at each applicable visit and for change from baseline to each applicable visit.

The following analyses of patient reported outcomes (PROs) also will be performed:

- Number and percentage of subjects who have ever experienced an increase from baseline up through each applicable timepoint of greater than or equal to 1/2 standard deviation (SD) at baseline points in the SF-36 MCS, PCS and SF-36 domain scores^{2,3}

TSQM Effectiveness, Side Effects, Convenience, and Global Satisfaction scores will be summarized descriptively at each applicable visit.

If a subject starts another treatment for HCV, then all PRO values for this subject measured on or after the start date of the new HCV treatment will be excluded from analyses.

11.0 Safety Analysis

11.1 General Considerations

Safety analyses will be performed using the safety population. Data will be summarized overall (across both arms).

11.2 Analysis of Adverse Events

Adverse events (AEs) will be coded using the Medical Dictionary for Regulatory Activities (MedDRA). The actual version of the MedDRA coding dictionary will be noted in the clinical study report.

11.2.1 Treatment-Emergent Adverse Events

Treatment-emergent AEs are defined as any AE with an onset date that is after the first dose of study drug and no more than 30 days after the last dose of study drug. Events where the onset date is the same as the study drug start date are assumed to be treatment-emergent. If an incomplete onset date was collected for an AE, the event will be assumed to be treatment-emergent, unless there is other evidence that confirms that the event was not treatment-emergent (e.g., the event end date was prior to the study drug start date).

11.2.2 Tabulations of Treatment-Emergent Adverse Events

The number and percentage of subjects with treatment-emergent AEs will be tabulated by primary MedDRA System Organ Class (SOC) and preferred term (PT). The SOCs will be presented in alphabetical order, and the preferred terms will be presented in alphabetical order within each SOC.

Subjects reporting more than one AE for a given PT will be counted only once for that term (most severe/highest grade incident for the severity tables and most related incident for the relationship tables). Subjects reporting more than one AE within a SOC will be counted only once for that SOC. Subjects reporting more than one AE will be counted only once in the overall total.

If a subject has an AE with unknown relationship, then the subject will be counted in the relationship category of "unknown," even if the subject has another occurrence of the same event with a relationship present. The only exception is if the subject has another occurrence of the same AE with a relationship assessment of "Reasonable Possibility." In this case, the subject will be counted under the "Reasonable Possibility" category.

Adverse Event Overview

An overview of AEs will be presented, consisting of the number and percentage of subjects experiencing at least one event for each of the following AE categories:

- Any treatment-emergent AE;
- Treatment-emergent AEs with a "reasonable possibility" of being related to DAAs (glecaprevir/pibrentasvir);
- Treatment-emergent AEs of grade 3 or higher;
- Treatment-emergent AEs of grade 3 or higher with a "reasonable possibility" of being related to DAAs (glecaprevir/pibrentasvir);
- Serious treatment-emergent AEs;
- Serious treatment-emergent AEs with a "reasonable possibility" of being related to DAAs (glecaprevir/pibrentasvir);

- Treatment-emergent AEs leading to discontinuation of study drug;
- DAA-related treatment-emergent AEs leading to discontinuation of study drug;
- Serious treatment-emergent AEs leading to discontinuation of study drug;
- Treatment-emergent AEs leading to interruption of study drug;
- Treatment-emergent AEs leading to death;
- Deaths.

Adverse Events by SOC and PT

The following summaries of AEs by SOC and PT will be generated:

- Treatment-emergent AEs;
- Serious treatment-emergent AEs;
- Serious treatment-emergent AEs with a "reasonable possibility" of being related to DAAs (glecaprevir/pibrentasvir);
- Treatment-emergent AEs leading to discontinuation of study drug;
- DAA-related treatment-emergent AEs leading to discontinuation of study drug;
- Treatment-emergent AEs leading to death.

A listing of treatment-emergent AEs grouped by SOC and preferred term with subject numbers will be created.

Adverse Events by Preferred Term

The following summaries of treatment-emergent AEs tabulated according to PT and sorted by the overall frequency across the two treatment arms will be generated:

- Treatment-emergent AEs;
- Treatment-emergent AEs with a "reasonable possibility" of being related to DAAs (GLE/PIB);

- Treatment-emergent AEs of Grade 3 or higher;
- Treatment-emergent AEs of Grade 3 or higher with a "reasonable possibility" of being related to DAAs (GLE/PIB).

Subjects reporting more than one AE for a given PT will be counted only once for that term (most severe/highest grade incident for the severity tables and most related incident for the relationship tables). Subjects reporting more than one AE will be counted only once in the overall total.

Adverse Events by Maximum Severity Grade Level

Treatment-emergent AEs and DAA-related treatment-emergent AEs will be summarized by maximum severity grade level of each preferred term. Each AE will be assigned a grade level (grade 1, 2, 3, 4, or 5) by the investigator. If a subject has an AE with unknown severity, then the subject will be counted in the severity grade level category of "unknown," even if the subject has another occurrence of the same event with a severity present. The only exception is if the subject has another occurrence of the same AE with the highest grade level (grade 5). In this case, the subject will be counted under the "Grade 5" category.

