6.1 Medical Complaints

The investigator will monitor each subject for clinical and laboratory evidence of adverse events on a routine basis throughout the study. The investigator will assess and record any adverse event in detail including the date of onset, event diagnosis (if known) or sign/symptom, severity, time course (end date, ongoing, intermittent), relationship of the adverse event to study drug, and any action(s) taken. For serious adverse events considered as having "no reasonable possibility" of being associated with study drug, the investigator will provide an "Other" cause of the event. For adverse events to be

considered intermittent, the events must be of similar nature and severity. Adverse events, whether in response to a query, observed by site personnel, or reported spontaneously by the subject will be recorded.

All adverse events will be followed to a satisfactory conclusion.

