6.1.3 Relationship to Study Drug

The investigator will use the following definitions to assess the relationship of the adverse event to the use of study drug:

Reasonable Possibility After consideration of factors including timing of the event, biologic plausibility, clinical judgment, and potential alternative causes, there is **sufficient** evidence (information) to suggest a causal relationship.

No Reasonable Possibility After consideration of factors including timing of the event, biologic plausibility, clinical judgment, and potential alternative causes, there is **insufficient** evidence (information) to suggest a causal relationship

For causality assessments, events assessed as having a reasonable possibility of being related to the study drug will be considered "associated." Events assessed as having no reasonable possibility of being related to study drug will be considered "not associated." In addition, when the investigator has not reported a causality or deemed it not assessable, AbbVie will consider the event associated.

[figure not shown]
If an investigator's opinion of no reasonable possibility of being related to study drug is given, an "Other" cause of event must be provided by the investigator for the serious adverse event.

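### AEs with unreported causality: Protocol 6.1.3 treats them as associated with study drug, but SAP 11.2.2 counts them as 'unknown', outside six relatedness summaries (minor)

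*SAP*

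**What the plan says.** **Protocol 6.1.3** gives the investigator two ratings, reasonable possibility and no reasonable possibility. It then states how they are classed: "events assessed as having a reasonable possibility of being related to the study drug will be considered" associated, and the other rating is not associated. For a missing rating it adds that "when the investigator has not reported a causality or deemed it not assessable, AbbVie will consider the event associated".

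**Protocol 8.1.6.1** commits to a tabulation of treatment-emergent AEs by relationship, with each subject counted at the most related occurrence of a term. It gives no rule for a missing relationship.

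**SAP 11.2.2** repeats the most-related rule and then adds: "If a subject has an AE with unknown relationship, then the subject will be counted in the relationship category of" 'unknown', even where another occurrence of the event has a rating. It continues: "The only exception is if the subject has another occurrence of the same AE with a relationship assessment of" 'Reasonable Possibility'.

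The same SAP section lists summaries restricted to AEs with a 'reasonable possibility' of being related to the DAAs. Others use a different term, such as the row "DAA-related treatment-emergent AEs leading to discontinuation of study drug" and the statement that "Treatment-emergent AEs and DAA-related treatment-emergent AEs will be summarized by maximum severity grade level of each preferred term".

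**SAP 12.1**, as shown, lists one change from the protocol: removal of the HCV/HIV co-infection analyses. The text directly after it was removed before review.

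**The concern.** Two documents give different classes to the same event. Under the protocol an AE with no causality rating belongs with the associated events. Under the SAP it belongs to a third class that Protocol 6.1.3 does not have.

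Safety is a primary objective (Protocol 4.1) and there is no control arm (Protocol 5.6.1), so rated relatedness is one of the main ways a reader can separate drug effects from background illness. A rule that can move drug-related counts in one direction only, downward, should either match the protocol or be declared as a departure. It should also be settled before the number of missing ratings is known.

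**Working it through.** The plan gives no figure for missing causality, so there is none to reproduce. The check has three steps.

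**1. Which summaries are touched.** Counting SAP 11.2.2 by label:
- 'Reasonable possibility': overview 3 (any, Grade 3 or higher, serious) + SOC/PT 1 (serious) + PT 2 (any, Grade 3 or higher) = 6.
- 'DAA-related': overview 1 (discontinuation) + SOC/PT 1 (discontinuation) + maximum grade 1 = 3.

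If 'DAA-related' is shorthand for the first label, nine summaries are touched. The SAP does not say.

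**2. Direction.** Under the protocol rule a related count covers subjects with a rated-related event plus subjects with a missing rating. Under the SAP rule it covers only the first group. The second count is a subset of the first, so it is equal or lower. The SAP exception does not alter this, because it concerns subjects who already have a related rating for the same AE.

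**3. Size.** Inputs are from Protocol Table 3 (N = 2,265). Scaling to 100 subjects is an assumption: that table excludes the CKD study, includes other durations, and does not say how missing causality was handled. Only subjects with the event but no related event can move into a row.
- Exposed per 100 = 100 × (all − related) / 2,265.
- Missing share that moves one expected subject = 1 / (exposed per 100).
- Expected shift = exposed per 100 × assumed missing share.

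| Row | All − related | Exposed per 100 | Share that moves one subject | Shift at 1% / 5% / 10% missing |
|---|---|---|---|---|
| Any AE | 1,529 − 929 = 600 | 26.49 | 3.8% | 0.26 / 1.32 / 2.65 |
| Grade ≥ 3 | 65 − 4 = 61 | 2.69 | 37.1% | 0.03 / 0.13 / 0.27 |
| SAE | 48 − 1 = 47 | 2.08 | 48.2% | 0.02 / 0.10 / 0.21 |
| Headache | 410 − 298 = 112 | 4.94 | 20.2% | 0.05 / 0.25 / 0.49 |

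Headache is the most exposed of the four preferred terms in Table 3. The SAE line is probably too high, because Protocol 6.1.3 requires a stated other cause when an SAE is judged unrelated. The documents give no missing share; 1%, 5% and 10% are assumptions, and zero is possible.

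For the any-related-AE row, take 41 of 100 (Table 3 gives 41.0%) and move one subject. The Wilson interval is [p + z²/2n ± z√(p(1−p)/n + z²/4n²)] / (1 + z²/n), with z = 1.96 and n = 100:
- 41/100: 31.9% to 50.8%.
- 42/100: 32.8% to 51.8%.

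**The case against.** The case for the SAP is a fair one, and much of it stands.

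- **Label.** A reader might infer that the protocol makes a missing rating a 'reasonable possibility', so that the SAP label should be redefined to include it. It does not. 'Reasonable possibility' is an investigator's judgement that the evidence is enough to suggest causation; 'associated' is the sponsor's classification. Only the second is applied to missing ratings. This stands and shapes the fix.
- **SAP convention.** One might cite SAP 11.2.1 ("If an incomplete onset date was collected for an AE, the event will be assumed to be treatment-emergent", absent contrary evidence) to argue that the causality rule breaks the SAP's own conservative practice. The closer parallel points the other way: SAP 11.2.2 puts missing severity in an 'unknown' category too, overridden only by the highest grade. The relationship rule also ranks 'unknown' above 'No Reasonable Possibility', so a missing rating is not absorbed as unrelated. Both points stand.
- **Visibility.** A reader might infer that the 'unknown' count would never be seen. The documents do not establish that. Protocol 8.1.6.1 commits to a relationship tabulation that could show it, although no summary listed in the SAP is described as doing so.
- **Function.** Protocol 6.1.3 sits among the AE recording rules, and 8.1.6.1 is silent on missing ratings, so the SAP could be said only to fill a gap. But 6.1.3 is not limited to expedited reporting, and the gap is filled against it.
- **Recoding before lock.** If missing ratings were set to associated before analysis, 'unknown' would be empty and the texts would agree. The SAP states no such step, and its explicit rule anticipates such records.
- **Rarity.** Protocol 6.1 requires the investigator to record, for any AE, the "relationship of the adverse event to study drug, and any action(s) taken". Few ratings should be missing. This stands and limits the size.

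**Conclusion.** The conflict holds: Protocol 6.1.3 and SAP 11.2.2 classify the same event differently, and the SAP rule can only leave related counts equal or lower. It is minor. The likely effect is zero to about one subject in 100 in the any-related-AE row, with almost the same interval either way, and a small fraction of a subject in the Grade 3 or higher and serious rows. That rests on the Table 3 scaling and on a missing share of no more than about 4%; at 10% the shift would be 2.6 subjects. All-cause AE, SAE and discontinuation counts, laboratory, vital-sign and Child-Pugh summaries, AE listings and all efficacy results are unaffected.

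A reader might infer that drug-related harm will be materially understated, or that the sponsor failed to declare the change. The documents support neither. No missing rate is given and relationship is to be recorded for any AE; and non-declaration can be stated only for SAP 12.1 as shown.

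**What to change.** In SAP 11.2.2, count AEs with missing or not-assessable causality as associated (DAA-related) in all relatedness-based summaries, in line with Protocol 6.1.3, and define 'DAA-related' once. Label those rows as including sponsor-imputed causality rather than widening the investigator rating 'reasonable possibility', and footnote the number of subjects so classified. If the sponsor prefers to keep 'unknown' as a separate class, declare and justify it in SAP 12.1 and show its count.

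The cost is a sentence or two, a row label, a footnote and a small programming change, best made before database lock. The downside is a slightly higher drug-related rate if any event lacks a rating.

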11.2.3 Adverse Events of Special Interest

Adverse events of special interest include the following:

- Hepatic decompensation/hepatic failure events, identified using the AbbVie Product MedDRA Query (PMQ) for Hepatic Decompensation and Hepatic Failure.
- Hepatocellular carcinoma events, identified using the preferred terms of hepatocellular carcinoma, hepatic neoplasm, hepatic cancer, hepatic cancer metastatic, and hepatic cancer recurrent.

For the hepatic decompensation/hepatic failure AE of special interest, the number and percentage of subjects experiencing at least one treatment-emergent AE in the search will

be presented by SOC and preferred term and across all SOCs/preferred terms. In addition, a by-subject listing of treatment-emergent AEs meeting the search criterion will be provided.

For the hepatocellular carcinoma AE of special interest, a by-subject listing of all post-baseline (i.e., including both treatment-emergent and non-treatment emergent) AEs meeting the search criterion will be provided.

11.2.4 Listings of Adverse Events

The following listings of AEs will be prepared:

- All serious AEs (from the time the subject signed the study-specific informed consent through the end of the study),
- Treatment-emergent serious AEs,
- Treatment-emergent AEs leading to discontinuation of study drug,
- Treatment-emergent AEs leading to study drug interruption,
- AEs (treatment-emergent or all, as applicable) in each of the AEs of special interest categories.

11.3 Analysis of Laboratory Data

Data collected from the central and local laboratories, including additional laboratory testing due to a serious AE, will be used in all analyses.

11.3.1 Variables and Criteria Defining Abnormality

Hematology variables to be summarized include: hematocrit, hemoglobin, red blood cell (RBC) count, white blood cell (WBC) count, neutrophils, bands, lymphocytes, monocytes, basophils, eosinophils, platelet count, prothrombin time (PT), international normalized ratio (INR), and activated partial thromboplastin time (aPTT).

Chemistry variables to be summarized include: blood urea nitrogen (BUN), creatinine, total bilirubin, direct and indirect bilirubin, alanine aminotransferase (ALT), aspartate

aminotransferase (AST), alkaline phosphatase, sodium, potassium, calcium, inorganic phosphorus, total protein, glucose, albumin, chloride, bicarbonate, magnesium, gamma-glutamyl transferase (GGT), creatinine clearance (calculated using Cockcroft-Gault), and eGFR by MDRD.

The definitions of toxicity grades for laboratory parameters are presented in [Table 10](#).

Table 10. Definitions of Toxicity Grades 1, 2, 3, and 4 for Laboratory Values

Test	Grade 1	Grade 2	Grade 3	Grade 4
ALT	> ULN – 3 × ULN	> 3 – 5 × ULN	> 5 – 20 × ULN	> 20 × ULN
AST	> ULN – 3 × ULN	> 3 – 5 × ULN	> 5 – 20 × ULN	> 20 × ULN
Alkaline Phosphatase	> ULN – 2.5 × ULN	> 2.5 – 5 × ULN	> 5 – 20 × ULN	> 20 × ULN
Total Bilirubin	> ULN – 1.5 × ULN	> 1.5 – 3 × ULN	> 3 – 10 × ULN	> 10 × ULN
Hemoglobin	< LLN – 100 g/L	< 100 – 80 g/L	< 80 g/L	--
Absolute Neutrophil Count	< LLN – 1.5 × 10 ⁹ /L	< 1.5 – 1.0 × 10 ⁹ /L	< 1.0 – 0.5 × 10 ⁹ /L	< 0.5 × 10 ⁹ /L
Platelet count	< LLN – 75.0 × 10 ⁹ /L	< 75.0 – 50.0 × 10 ⁹ /L	< 50.0 – 25.0 × 10 ⁹ /L	< 25.0 × 10 ⁹ /L
INR	> 1 – 1.5 × ULN	> 1.5 – 2.5 × ULN	> 2.5 × ULN	--
Creatinine clearance	< LLN – 60 mL/min	< 60 – 30 mL/min	< 30 – 15 mL/min	< 15 mL/min
Albumin	< LLN – 30 g/L	< 30 – 20 g/L	< 20 g/L	--
White blood cells	< LLN – 3.0 × 10 ⁹ /L	< 3.0 – 2.0 × 10 ⁹ /L	< 2.0 – 1.0 × 10 ⁹ /L	< 1.0 × 10 ⁹ /L
Lymphocyte	< LLN – 0.8 × 10 ⁹ /L	< 0.8 – 0.5 × 10 ⁹ /L	< 0.5 – 0.2 × 10 ⁹ /L	< 0.2 × 10 ⁹ /L
GGT	> ULN – 2.5 × ULN	> 2.5 – 5 × ULN	> 5 – 20 × ULN	> 20 × ULN
Glucose (high)	> ULN – 8.9 mmol/L	> 8.9 – 13.9 mmol/L	> 13.9 – 27.8 mmol/L	> 27.8 mmol/L
Glucose (low)	< LLN – 3.0 mmol/L	< 3.0 – 2.2 mmol/L	< 2.2 – 1.7 mmol/L	< 1.7 mmol/L
Creatinine	> ULN – 1.5 × ULN	> 1.5 – 3 × ULN	> 3 – 6 × ULN	> 6 × ULN
Cholesterol	> ULN – 7.75 mmol/L	> 7.75 – 10.34 mmol/L	> 10.34 – 12.92 mmol/L	> 12.92 mmol/L
aPTT	> ULN – 1.5 × ULN	> 1.5 – 2.5 × ULN	> 2.5 × ULN	--
Sodium (low)	< LLN – 130 mmol/L	--	< 130 – 120 mmol/L	< 120 mmol/L
Sodium (high)	> ULN – 150 mmol/L	> 150 – 155 mmol/L	> 155 – 160 mmol/L	> 160 mmol/L
Potassium (low)	< LLN – 130 mmol/L	--	< 130 – 120 mmol/L	< 120 mmol/L
Potassium (high)	> ULN – 5.5 mmol/L	> 5.5 – 6.0 mmol/L	> 6.0 – 7.0 mmol/L	> 7.0 mmol/L
Magnesium (low)	< LLN – 0.5 mmol/L	< 0.5 – 0.4 mmol/L	< 0.4 – 0.3 mmol/L	< 0.3 mmol/L
Magnesium (high)	> ULN – 1.23 mmol/L	--	> 1.23 – 3.30 mmol/L	> 3.30 mmol/L

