11.3.2 Statistical Methods

The baseline value for clinical laboratory tests will be the last non-missing measurement on or before the day of the first dose of study drug. Values on Day 1 must also be before the time of first dose if time is available. The same baseline value will be used for changes at Treatment Period visits and changes at Post-Treatment Period visits.

Changes from baseline to each post-baseline visit, including applicable post-treatment visits, will be summarized. Each protocol-specified laboratory parameter will be summarized with the sample size, baseline mean; visit mean; and change from baseline mean, standard deviation, minimum, median, and maximum.

Individual changes in the laboratory parameters listed in Section 11.3.1 will be tabulated using shift tables. Laboratory data values will be categorized as low, normal, or high based on normal ranges of the laboratory used for each sample. Shift tables from baselineto minimum value and maximum value during the Treatment Period will be created. For each parameter, the shift tables will cross tabulate the frequency of subjects with baseline values below/within the normal range to maximum above the normal range and with baseline values within/above the normal range to minimum below the normal range.

The laboratory parameters listed in Table 11 will be assigned a toxicity grade of 1, 2, 3, or 4. The number and percentage of subjects with a maximum toxicity grade of 1, 2, 3 or 4 will be tabulated. To be counted, the post-baseline value must have a toxicity grade that is more extreme than the toxicity grade corresponding to the baseline value. For each laboratory parameter in Table 11, the summary will also include the number and percentage of subjects with a maximum of at least grade 3. A listing of all relevant laboratory parameters will be provided for each subject who had an increase to grade 2 or higher for any laboratory variable in Table 11.

Assessment of Hepatic Laboratory Values

The number and percentage of subjects with laboratory values meeting the following criteria during treatment will be summarized:

- Post-nadir (preceding value is lower than the subsequent value) ALT $> 5 \times \text{ULN}$ (regardless of grade change);
- Total bilirubin $\geq 2 \times \text{ULN}$ and $>$ baseline (i.e., a post-baseline value must be more extreme than the baseline value to be considered);
- Post-nadir ALT $> 3 \times \text{ULN}$ and total bilirubin $> 2 \times \text{ULN}$;

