11.4 Analysis of Vital Signs and Weight

11.4.1 Variables and Criteria Defining Abnormality

Vital sign variables are body temperature, sitting systolic blood pressure, sitting diastolic blood pressure, sitting pulse rate, and body weight.

The criteria for potentially clinically significant (PCS) vital sign findings are presented in [Table 11](#).

Table 11. Criteria for Potentially Clinically Significant Vital Sign Values

Test/Measurement	Very Low (VL)	Very High (VH)
Systolic Blood Pressure	≤ 90 mmHg AND A decrease of ≥ 20 mmHg from baseline	≥ 180 mmHg AND An increase of ≥ 20 mmHg from baseline
Diastolic Blood Pressure	≤ 50 mmHg AND A decrease of ≥ 15 mmHg from baseline	≥ 105 mmHg AND An increase of ≥ 15 mmHg from baseline
Pulse Rate	≤ 50 bpm AND A decrease of ≥ 15 bpm from baseline	≥ 120 bpm AND An increase of ≥ 15 bpm from baseline
Weight	A decrease of ≥ 15% from baseline	An increase of ≥ 15% from baseline
Body Temperature		> 38.3°C AND An increase of ≥ 1.1°C from baseline

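### SAP Table 10 grades low potassium with the low-sodium cut-offs (130 and 120 mmol/L), so its toxicity-grade line comes out either empty or entirely Grade 4

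*SAP*

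**What the plan says.** Table 10 in SAP Section 11.3.1 defines the laboratory toxicity grades. Its low-potassium row begins "Potassium (low) < LLN – 130 mmol/L", leaves Grade 2 blank, puts Grade 3 between 130 and 120 mmol/L, and puts Grade 4 below 120 mmol/L. The low-sodium row begins "Sodium (low) < LLN – 130 mmol/L" and continues identically. The high-potassium row begins "Potassium (high) > ULN – 5.5 mmol/L" and then steps at 6.0 and 7.0 mmol/L.

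Section 11.3.2 sets the counting rule: "To be counted, the post-baseline value must have a toxicity grade that is more extreme than the toxicity grade corresponding to the baseline value". It asks for three outputs built on the grades:

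- Grade assignment and a maximum-grade table: "The laboratory parameters listed in Table 11 will be assigned a toxicity grade of 1, 2, 3, or 4".
- A count of subjects reaching at least Grade 3: "For each laboratory parameter in Table 11, the summary will also include the number and percentage of subjects".
- A listing of subjects with "an increase to grade 2 or higher for any laboratory variable in Table 11".

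All three cite Table 11. In Section 11.4.1 that table is titled "Table 11. Criteria for Potentially Clinically Significant Vital Sign Values".

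On the protocol side, Section 8.1.6.2 promises a summary of the shift from baseline to the worst post-baseline CTCAE grade for laboratory values, and Section 6.1.7 names CTCAE version 4 as the standard for grading laboratory abnormalities.

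**The concern.** A potassium value cannot sensibly be Grade 4 low below 120 mmol/L and Grade 4 high above 7.0 mmol/L. The contradiction is inside the SAP's own table, so no outside reference is needed to see it. Sodium limits appear to have been copied into the potassium row.

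The row drives a planned safety output. Safety is part of the primary objective, potassium is a protocol-specified test, and eligibility extends to all CKD stages and to dialysis. If the table is programmed as written, the low-potassium line of the grade summary, its at-least-Grade-3 count and its trigger for the Grade 2 or higher listing are all wrong. The error could hide every case or label every case as the most severe.

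**Working it through.** The plan states no figure to reproduce, so this is a logic check on the table and the counting rule.

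**1. Row comparison (SAP Table 10, mmol/L)**

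| Row | Grade 1 | Grade 2 | Grade 3 | Grade 4 |
|---|---|---|---|---|
| Sodium, low | LLN to 130 | blank | 130 to 120 | below 120 |
| Potassium, low | LLN to 130 | blank | 130 to 120 | below 120 |
| Potassium, high | ULN to 5.5 | 5.5 to 6.0 | 6.0 to 7.0 | above 7.0 |

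The two low rows agree in 4 of 4 cells.

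**2. Order check.** Four analytes have both a low and a high row. The highest low cut-off should lie below the lowest high cut-off:

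- glucose: 3.0 < 8.9, holds
- sodium: 130 < 150, holds
- magnesium: 0.5 < 1.23, holds
- potassium: 130 > 5.5, fails

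The potassium Grade 4 low limit is 120 / 7.0 = 17 times its Grade 4 high limit.

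**3. Reading 1: numeric cut-offs applied literally.** Any value below 120 is Grade 4, which takes in every plausible potassium result, at baseline as well as later. A post-baseline grade can then never exceed the baseline grade. On an assumed grid of 66 values (1.5 to 8.0 mmol/L in steps of 0.1), all 66 are Grade 4, and 0 of 66 × 66 = 4,356 baseline/post-baseline pairs satisfy the counting rule. The line is empty, and low potassium never triggers the Grade 2 or higher listing.

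**4. Reading 2: a value must first be below LLN, then the cut-offs apply.** A value at or above LLN gets no grade, and any value below LLN is also below 120 and so is Grade 4. The pairs counted are (grid values below LLN) × (grid values at or above LLN). The documents give no LLN, so three are assumed:

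| Assumed LLN | Below × at or above | Pairs counted | Grade of counted pairs |
|---|---|---|---|
| 3.0 | 15 × 51 | 765 | all 4 |
| 3.5 | 20 × 46 | 920 | all 4 |
| 4.0 | 25 × 41 | 1,025 | all 4 |

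No pair with a baseline already below LLN is counted, because that baseline is already Grade 4.

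**5. Independent repeat.** A separate check used a grid from 2.0 to 8.0 mmol/L, assumed LLNs of 3.0, 3.3, 3.5, 3.8 and 4.0, and three codings: literal with the worst grade first, interval matching, and LLN first. Literal and interval coding counted nothing at every LLN. LLN-first coding produced only ungraded values or Grade 4. As a control, the same row was run on sodium with an assumed LLN of 135: values of 138, 133, 128 and 118 graded as 0, 1, 3 and 4. The row works for sodium and fails for potassium.

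**6. Table references.** Table 11 covers systolic pressure, diastolic pressure, pulse, weight and temperature. It holds five vital-sign measures and no laboratory test.

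**The case against.** The best case on the other side is about proportion. This is one copied row of 24 in a descriptive safety table with no hypothesis test. The error is conspicuous, and the protocol already fixes the intended standard as CTCAE version 4, so a careful programmer would probably notice. Section 11.3.1 says that the laboratory grades are in Table 10, so the Table 11 references are unlikely to mislead anyone. The pair counts describe an assumed grid and say nothing about how many subjects would be affected. Reading 1 is strained, because it ignores the below-LLN entry condition and makes 8.0 mmol/L both Grade 4 low and Grade 4 high.

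Much of this is fair, and it limits the scope. The grid counts only illustrate the logic, and all-Grade-4 means all counted subjects. Other results are possible if Grade 1 is coded simply as below LLN, or if a missing baseline is treated as ungraded under the literal reading; the first departs from the table, and the SAP has no rule for the second. It would also be wrong to lean on SAP Section 12.1, which mentions only the HIV co-infection analyses: a copying slip is not something that section would list.

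None of this makes the row usable. A silent correction by the programmer would leave the output inconsistent with the SAP. The fallback displays are also partial. The normal-range shift tables show no severity and, for falls, include only baselines within or above range. Under protocol Section 6.1.1.1 a laboratory abnormality becomes an adverse event only if it leads to discontinuation, needs treatment, or the investigator judges it to be one. Change-from-baseline summaries still include potassium but do not grade it.

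**Conclusion.** Wrong as written. The low-potassium row of Table 10 carries the low-sodium limits, and under the counting rule in Section 11.3.2 the low-potassium grade line is either empty or has every counted subject at Grade 4. Grades 1 to 3 are unreachable under both readings.

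The effect is confined to that line of the grade summary, its at-least-Grade-3 count and its listing trigger. SVR12, the mean changes and the normal-range shift tables do not use Table 10. The conclusion rests on potassium values being in single digits, as the high-potassium row implies, and held for every LLN tried from 3.0 to 4.0 mmol/L. The documents give no LLN and no potassium data, so the number of subjects affected cannot be stated. It should be fixed, because following the plan gives a wrong safety result and the correction is nearly free.

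**What to change.** Three edits before the grade tables are programmed or finalised:

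1. Reconcile the low-potassium row of Table 10 with the CTCAE version 4 grading that protocol Section 6.1.7 names. The documents do not reproduce those limits, so they should be taken from that source; none are suggested here.
2. In SAP Section 11.3.2, change the three references to Table 11 for laboratory grading (grade assignment, at-least-Grade-3 count, Grade 2 or higher listing) to Table 10. The Table 11 references in Section 11.4 for vital signs are correct and stay.
3. Check that the grading program uses the corrected row.

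The cost is one table row, three cross-references and one programming check, with no change to data collection.
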